### **20.4 OTHER ENDPOINT ANALYSES**

The frequency and proportion of medical and lens findings and adverse events will be presented for first and second eyes of toric and control subjects. The severity of all serious adverse events and adverse device effects, such as IOL repositioning procedures, through 6 months postoperatively will also be presented.

## 20.5 ADDITIONAL ANALYSES AND DATA CONVENTIONS

For categorical data, frequencies and proportions will be computed. Descriptive statistics will include sample size (N), mean, standard deviation (SD), minimum (Min) and maximum (Max) as appropriate.

## 20.6 SAMPLE SIZE

A sample size of a minimum of 396 enrolled subjects to achieve bilateral implantation of approximately 294 subjects: 169 TECNIS Toric ZCT300 and ZCT400 and 125 control subjects is reflective of the number of subjects enrolled on the date of this protocol revision (3.0).

A two-group large-sample normal approximately test of proportions with a one-sided 0.05 significance level using only 37 evaluable toric subjects and 27 evaluable control subjects will have a greater than 90% power to detect a rate of severe visual distortions for toric subjects as being 10 percentage points or greater than that for control subjects. This assumes severe visual distortion rates of 1% for both the toric and control subjects. Therefore, the sample size proposed for a minimum of 396 enrolled subjects, assuming a 10% drop out rate for a minimum of 152 toric and 112 control subjects available for evaluation at 6 months, is sufficient to demonstrate non-inferiority in the rate of severe visual distortions (the primary endpoint of this study) between the two study groups in a larger population in clinical practice and thereby demonstrate the continued safety of the toric IOLs.

## 20.7 DATA REPORTING REQUIREMENTS

Interim status study reports will be provided to FDA every 6 months from the date of study initiation for the first 2 years and annually thereafter according to the guidance document entitled "Procedures for Handling Post-Approval Studies Imposed by PMA Order," dated June 15, 2009.

A primary-analysis, complete 6-month study report will be provided to FDA approximately 3 months following completion of the last 6-month study visit. Any 1-year data collected to date will be included.

A final study report will be provided to FDA approximately 3 months following completion of the last 1-year study visit. Note that the primary-analysis, 6-month report and the final report may be submitted at the same time depending upon when the last 6-month and 1-year exams are completed.

Interim and final study reports will include general enrollment and accountability items including the number of active sites, the number of subjects enrolled, implanted and discontinued and the number of postoperative examinations completed. Enrollment rates and subject follow-up will be compared to anticipated, target study timelines (Section 10.0 Study Timeline).

## **21.0 REFERENCES**

1. Ferrer-Blasco, T. et al. Prevalence of corneal astigmatism before cataract surgery. *J Cataract Refract Surg* 2009; 35: 70-75
2. Hoffer KJ. Biometry of 7,500 cataractous eyes. *Am J Ophthalmol* 1980;90:360-368

**APPENDIX A  
SUMMARY OF EXAMINATIONS FOR EACH VISIT**

Examination X= To be performed A= To be performed if a subject reports a severe visual distortion or experienced an ocular adverse event at this visit B= To be performed if a visual distortion is spontaneously reported prior to 6 month exam or prior to a required IOL repositioning (adverse event) O = Only if medically indicated	Preoperative Both eyes	Op 1 1st eye	Op 2 2nd eye	Unscheduled Visit	1 Month Both eyes	6 Months Both eyes	1 Yeara Both eyes
Ocular history, inclusion/exclusion criteria	X						
Informed consent	X						
Potential visual acuity	X						
Targeted refraction/IOL power calculations b /axial length	X						
Lens power/serial number/operative procedures		X	X				
Manifest refraction (Snellen)	X			A	A	A	X
UCDVA-photopic, monocular (Snellen)	X			A	A	A	X
UCDVA-photopic, binocular (Snellen)						A	X
BCDVA-photopic, monocular (Snellen)	X			A	A	A	X
BCDVA-photopic, binocular (Snellen)						A	X
Offer spectacle and/or contact lens prescription					X		
Keratometry	X			B d	B d	X d	X d
Intraocular pressure	X			A	A	A	X
Biomicroscopic slit-lamp exam c	X			A	A	X	X
Toric IOL axis measurement at dilated slit-lamp exam d ,				B d	B d	X d	X d
Dilated fundus exam	X			O	O	O	O
Adverse events		X	X	X	X	X	X
Ocular medications	X			X	X	X	X
Subject questionnaire	X			B	B	X	X

a Examination at 1 year is to be conducted ONLY if a subject reported a severe visual distortion at 6 months or if the subject experienced an IOL repositioning procedure (due to IOL misalignment) during the study.  
b Includes documentation of toric IOL calculations showing ZCT300 and/or ZCT400 IOLs as toric choices for each eye  
c Includes determination of medical and lens findings/complications, including lens rotation  
d For Toric IOLs only

**APPENDIX B  
STUDY QUESTIONNAIRE**

# Patient Reported Visual Distortions Questionnaire (PRVDQ)

---

This questionnaire asks about the severity of visual distortions **OVER THE LAST 7 DAYS**. If your vision is different between eyes, please respond with how you see with both eyes in general. For each question, please indicate if you have experienced the “visual distortion” under these **3 circumstances**:

- A. When **NOT** wearing corrective glasses (including reading glasses) or contacts
- B. When **WEARING** corrective glasses (including reading glasses) or contacts.
- C. Overall (taking all things into account)

Please read each question carefully and answer as honestly as you can without the help of anyone. There are no right or wrong answers.

For ALL questions, please mark an  in the box that best describes your answer.

**Blurred vision at all distances** may be described as a lack of vision sharpness resulting in the inability to see fine detail.

Q1. Please rate the severity of **blurred vision at all distances** you experienced over the LAST 7 DAYS...

	Did not experience	Mild	Moderate	Severe	Does not Apply
	▼	▼	▼	▼	▼
a. When not wearing corrective glasses or contacts (including reading glasses).....	 0	 1	 2	 3	 4
b. When wearing corrective glasses or contacts (including reading glasses) .....	 0	 1	 2	 3	 4
c. Overall (taking all things into account).....	 0	 1	 2	 3	

**Hazy vision** may be described as looking through fog or smoke.

Q2. Please rate the severity of **hazy vision** you experienced over the LAST 7 DAYS...

	Did not experience	Mild	Moderate	Severe	Does not Apply
	▼	▼	▼	▼	▼
a. When not wearing corrective glasses or contacts (including reading glasses).....	 0	 1	 2	 3	 4
b. When wearing corrective glasses or contacts (including reading glasses) .....	 0	 1	 2	 3	 4
c. Overall (taking all things into account).....	 0	 1	 2	 3	

**Double vision** may be described as seeing a single object as two slightly overlapping or separate objects.

Q3. Please rate the severity of **double vision** you experienced over the LAST 7 DAYS...

	Did not experience	Mild	Moderate	Severe	Does not Apply
	▼	▼	▼	▼	▼
a. When not wearing corrective glasses or contacts (including reading glasses).....	 0	 1	 2	 3	 4
b. When wearing corrective glasses or contacts (including reading glasses) .....	 0	 1	 2	 3	 4
c. Overall (taking all things into account).....	 0	 1	 2	 3	

---

Straight lines may appear to **slant, tilt, split or separate**.

Q4. Please rate the severity of **seeing lines that slant, tilt, split or separate** you experienced, over the LAST 7 DAYS...

	Did not experience	Mild	Moderate	Severe	Does not Apply
	▼	▼	▼	▼	▼
a. When not wearing corrective glasses or contacts (including reading glasses).....	 0	 1	 2	 3	 4
b. When wearing corrective glasses or contacts (including reading glasses) .....	 0	 1	 2	 3	 4
c. Overall (taking all things into account).....	 0	 1	 2	 3	

Lines or edges of an object may appear to have **dark bumps or spikes**.

Q5. Please rate the severity of seeing **lines or edges of an object with dark bumps or spikes** you experienced over the LAST 7 DAYS...

Did not experience	Mild	Moderate	Severe	Does not Apply
▼	▼	▼	▼	▼

- a. When **not** wearing corrective glasses or contacts (including reading glasses).....  0 .....  1 .....  2 .....  3 .....  4
- b. When **wearing** corrective glasses or contacts (including reading glasses) .....  0 .....  1 .....  2 .....  3 .....  4
- c. Overall (taking all things into account).....  0 .....  1 .....  2 .....  3

**Flat surfaces may appear curved.**

Q6. Please rate the severity of **flat surfaces appearing curved** you experienced over the LAST 7 DAYS...

Did not experience	Mild	Moderate	Severe	Does not Apply
▼	▼	▼	▼	▼

- a. When **not** wearing corrective glasses or contacts (including reading glasses).....  0 .....  1 .....  2 .....  3 .....  4
- b. When **wearing** corrective glasses or contacts (including reading glasses) .....  0 .....  1 .....  2 .....  3 .....  4
- c. Overall (taking all things into account).....  0 .....  1 .....  2 .....  3

Objects may appear to be a **different color or shade of the same color** than you know they actually are.

Q7. Please rate the severity of objects appearing to be a **different color or shade of the same color** than you know they actually are over the LAST 7 DAYS...

	Did not experience	Mild	Moderate	Severe	Does not Apply
	▼	▼	▼	▼	▼

a. When **not** wearing corrective glasses or contacts (including reading glasses).....  0.....  1.....  2.....  3.....  4

b. When **wearing** corrective glasses or contacts (including reading glasses) .....  0.....  1.....  2.....  3.....  4

c. Overall (taking all things into account).....  0.....  1.....  2.....  3

---

Objects may appear to **project or stand out from the background in an unusual way.**

Q8. Please rate the severity of objects appearing to **project or stand out from the background in an unusual way** you experienced over the LAST 7 DAYS...

	Did not experience	Mild	Moderate	Severe	Does not Apply
	▼	▼	▼	▼	▼

a. When **not** wearing corrective glasses or contacts (including reading glasses).....  0.....  1.....  2.....  3.....  4

b. When **wearing** corrective glasses or contacts (including reading glasses) .....  0.....  1.....  2.....  3.....  4

c. Overall (taking all things into account).....  0.....  1.....  2.....  3

**Objects may appear to be further or closer** than they actually are, making it difficult to judge distance.

Q9. Please rate the severity of **objects appearing further or closer** than they actually are over the LAST 7 DAYS...

Did not experience	Mild	Moderate	Severe	Does not Apply
▼	▼	▼	▼	▼

- a. When **not** wearing corrective glasses or contacts (including reading glasses) .....  0 .....  1 .....  2 .....  3 .....  4
- b. When **wearing** corrective glasses or contacts (including reading glasses) .....  0 .....  1 .....  2 .....  3 .....  4
- c. Overall (taking all things into account).....  0 .....  1 .....  2 .....  3

Objects may appear distorted causing their **size or shape** to look different than you know they actually are.

Q10. Please rate the severity of objects appearing to have a **different size or shape** than you know they actually are over the LAST 7 DAYS...

Did not experience	Mild	Moderate	Severe	Does not Apply
▼	▼	▼	▼	▼

- a. When **not** wearing corrective glasses or contacts (including reading glasses) .....  0 .....  1 .....  2 .....  3 .....  4
- b. When **wearing** corrective glasses or contacts (including reading glasses) .....  0 .....  1 .....  2 .....  3 .....  4
- c. Overall (taking all things into account).....  0 .....  1 .....  2 .....  3

Visual distortions may cause **physical discomfort** such as nausea (feeling sick to your stomach), dizziness and/or headache.

Q11. Please rate the severity of **physical discomfort** related to vision you experienced over the LAST 7 DAYS...

Did not experience	Mild	Moderate	Severe	Does not Apply
▼	▼	▼	▼	▼

- a. When **not** wearing corrective glasses or contacts (including reading glasses).....  0 .....  1 .....  2 .....  3 .....  4
- b. When **wearing** corrective glasses or contacts (including reading glasses) .....  0 .....  1 .....  2 .....  3 .....  4
- c. Overall (taking all things into account).....  0 .....  1 .....  2 .....  3

Q12. Over the LAST 7 DAYS, have you experienced any other visual distortions not described above?

- Yes (if yes, please describe): \_\_\_\_\_
- No

## APPENDIX C

### TORIC IOL AXIS MEASUREMENT AT SLIT LAMP

The following instructions are to be followed for the measurement of the toric IOL axis in both eyes.

1. Dilate each eye with 2.5% phenylephrine prior to measurement. Tropicamide (1%) may be used in addition, at the Investigator's discretion.
2. Allow sufficient time to achieve adequate pupillary dilation to facilitate direct visualization of alignment marks.
3. At the slit lamp, adjust the slit-lamp beam to be as narrow as possible and align the beam with the four axis orientation marks (4.5, 5.0, 5.5 and 6.0 mm diameter) on one side of the toric IOL.
  - a. It is important to align the beam with at least two of the four orientation marks for an accurate measurement.
  - b. Ensure the subject's head is oriented vertically in the slit lamp with proper head position and alignment of eye with the slit lamp.
4. Read the angle of the toric IOL axis markers based on the narrowed slit-lamp beam from the angular scale on the slit lamp.
5. Record this angle in degrees for each eye on the appropriate postoperative case report form.

## APPENDIX D SLIT-LAMP EXAM RATINGS

### A. RATINGS OF AQUEOUS CELLS AND FLARE

For consistency across study sites, the SUN (Standardization of Uveitis Nomenclature) Working Group Grading Scheme is to be used for grading of anterior chamber cells and flare as reported in: Standardization of uveitis nomenclature for reporting clinical data. Results of the first international workshop; The standardization of uveitis nomenclature (SUN) working group. Am J Ophthalmol 2005;140:509-516.

#### CELLS

Grade	Cells in Field*	<small>Field is a 1x1 mm slit beam</small>
0	<1	
0.5+	1-5	
1+	6-15	
2+	16-25	
3+	26-50	
4+	>50	

#### FLARE

Grade	Description
0	None
1+	Faint
2+	Moderate (iris and lens details clear)
3+	Marked (iris and lens details hazy)
4+	Intense (fibrin or plastic aqueous)

### B. RATINGS OF CORNEAL EDEMA

Corneal edema should be classified according to the haziness of the epithelium, the number of microcysts observed and the clouding of the stroma.

None	0	Normal transparency: a. No epithelial or sub-epithelial haziness b. No microcysts c. No stromal cloudiness
Trace	+1	a. Barely discernable localized epithelial or sub-epithelial haziness and/or b. 1 to 20 microcysts and/or c. Barely discernable localized stromal cloudiness
Mild	+2	a. Faint but definite localized or generalized epithelial, sub-epithelial or stromal haziness/cloudiness and/or b. 21-50 microcysts
Moderate	+3	a. Significant localized or generalized epithelial, sub-epithelial or stromal haziness/cloudiness and/or b. 51-100 microcysts
Severe	+4	a. Definite widespread epithelial or stromal cloudiness, giving dull glass appearance to cornea or numerous coalescent bullae (please note the number and location of bullae) and/or b. >100 microcysts or bullae and/or c. Numerous striae (please note the number and location of striae or folds)

## APPENDIX D (CONTINUED) SLIT-LAMP EXAM RATINGS

### C. POSTERIOR CAPSULE STRIAE GRADING SCALE

The following five-point grading scale is to be used for rating striae in the posterior capsule:

None	0	None
Trace	+1	One detectable, barely noticeable striae
Mild	+2	One or two prominent striae
Moderate	+3	Three or more prominent striae, but visibility of retina is not impacted
Severe	+4	Three or more prominent striae affecting visualization of retina

### D. POSTERIOR CAPSULE OPACIFICATION (PCO) GRADING SCALE

Below is the five-point grading scale to be used for PCO determination:

None	0	Normal posterior capsule with no area of opacity. Red reflex bright.
Trace	+1	Some loss of transparency involving the posterior capsule. Red reflex fairly bright
Mild	+2	Mild loss of transparency with cloudiness extending through most of the posterior capsule. There may be a few Elschnig's pearls in the posterior capsule. Red reflex mildly diminished.
Moderate	+3	Moderate loss of transparency with difficulty visualizing the retina. There may be multiple Elschnig's pearls in the posterior capsule. Red reflex markedly diminished.
Severe	+4	Posterior capsule very opaque with inability to view the retina. The posterior capsule may have confluent Elschnig's pearls and fibrous scarring. Red reflex barely visible.

### E. IOL GLISTENINGS

Use the following scale to grade IOL glistenings using a slit beam 2.0 mm wide and 10.0 mm long:

None	0	No glistenings visible
Rare	+0.5	<10 glistenings visible
Trace	+1	10-19 glistenings visible
Mild	+2	20-29 glistenings visible
Moderate	+3	30-39 glistenings visible
Severe	+4	≥40 glistenings visible

## APPENDIX E ADVERSE EVENT REPORTING INSTRUCTIONS

### **Adverse Device Effect (ADE)**

In the event of an ADE, the investigator must notify AMO preferably within 48 hours and no later than 10 working days of first becoming aware of the event by completing the Adverse Event Form and submitting it to AMO.

### **Serious Adverse Event (SAE)**

In the event of a sight- or life-threatening incident or serious adverse event, which may or may not be related to use of the study device, **the investigator must notify AMO immediately (no later than 48 hours after detection)** by phone and/or email and by submitting a completed Adverse Event Form as follows:

- a. Contact the following AMO personnel by phone:

**AND**

- b. Complete an Adverse Event Form and submit to AMO.

### **Unanticipated Adverse Device Effect (UADE)**

For an adverse event that may reasonably be regarded as product related and was not previously expected in nature, severity, or degree of incidence in the study protocol, risk management file or existing product labeling, the investigator must report the event to AMO within 48 hours of detection after learning of the event using the same reporting method as for SAEs.

### **Device Defect or Malfunction without an Adverse Event**

In the event of a complaint of study device defect or malfunction, the investigator must notify AMO preferably within 48 hours and no later than 10 working days of first becoming aware of the event by completing the information about the device on the Operative CRF and submitting it to AMO.

---

*SAMPLE ONLY - NOT TO BE USED FOR SUBJECT ENROLLMENT*

Statistical Analysis Plan

POST-APPROVAL STUDY OF THE TECNIS® TORIC IOL, MODELS ZCT300 AND ZCT400

NCT Number: NCT02566083

Document date: 24 Jun 2015

STATISTICAL ANALYSIS PLAN

Protocol

TIOL-202-TPAS

POST-APPROVAL STUDY OF THE TECNIS® TORIC IOL, MODELS ZCT300 AND ZCT400

1. Introduction

This document summarizes the statistical methods to be implemented during the analysis of data for the post-approval study of the TECNIS® Toric IOL models ZCT300 and ZCT400. The purpose of this study is to evaluate the rates of severe visual distortions for the TECNIS Toric IOLs with >2.0 D of cylinder correction at the corneal plane in a larger population in clinical practice compared to a control (model ZCB00). This study will be a prospective, multicenter, bilateral, open-label, parallel group clinical investigation. Subjects are to be bilaterally implanted with the toric ZCT (models ZCT300 and ZCT400) or the control ZCB00 IOL.

The key timeframe for analysis will be the six month visit. The primary endpoint for this study is the rate of severe visual distortions defined as the proportion of subjects who report a severe visual distortion under overall circumstances at 6 months for any of the following 5 visual distortion items of interest:

- •lines that slant, tilt, split or separate
- •flat surfaces appearing curved
- •objects appearing further away or closer than they actually are
- •objects appearing to have a different size or shape
- physical discomfort related to vision

For the primary endpoint, severe visual distortions will be assessed using the overall circumstance reply at the 6 month visit. For the primary endpoint, the frequency and proportion of subjects reporting one or more of these items as severe will be used to determine the rate of severe visual distortions.

Results from individual visual distortion items on the PRVDQ questionnaire will also be reported for overall and with and without correction..

Other endpoints include: rates of IOL repositioning procedures (secondary surgical intervention) due to IOL misalignment and rates of other adverse events.

2. Analysis Populations and Data Conventions

2.1 Analysis Population

For questionnaire data, the primary analysis population will be all subjects implanted binocularly with a toric ZCT or control ZCB00 IOL and having available data at the six month visit or at a prior postoperative visit with questionnaire data carried forward. In addition, data for severe visual distortions (based on the 5 defined items) will also be reported for all bilateral subjects and those with only one eye implanted and the fellow eye having phakic status, a cataract, or another IOL. For questionnaire data, subjects with missing data for symptoms of visual distortion at the six month visit will have the last reported value carried forward if the subject had an earlier visit unless the subject had an IOL repositioning procedure or IOL removal in which case the last reported postoperative visual distortion data available prior to the repositioning/removal procedure will be used.

For severe visual distortions (based on the 5 defined items) an additional analysis population will be evaluated that includes all subjects with last observation carried forward for missing data as described above as well as use of data imputation for

subjects with no available data at any time point. Imputation for those with no data will be performed using MCMC multiple imputation techniques as described in Little & Rubin¹ and implemented using the MI and MIANALYZE procedures² in SAS® (Version 9.4). The degree of missingness for severe visual distortions based on the 5 defined items will be reported. Sensitivity analyses will be performed for severe visual distortions based on the 5 defined items for the final data analysis to evaluate missing at random assumptions.

Data will be primarily reported for both toric IOL models pooled and for all controls, however, for severe visual distortions (based on the 5-items), analyses will also include reporting the data separately for bilateral subjects in the lower-cylinder group (those implanted with the ZCT300) and the higher-cylinder group (those implanted with the ZCT400). Control subjects will be included in the lower- or higher-cylinder groups based on the toric lens they would have received if they had chosen to get a ZCT IOL. Subjects who have a lower-cylinder IOL in one eye (e.g. ZCT300) and a higher-cylinder IOL in the fellow eye (e.g. ZCT400) will be placed in the higher-cylinder group for analysis.

Adverse events will be reported for all study eyes and reported by IOL model for first and second eyes.

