**VISITS AND PROCEDURES:**

All subjects enrolled in the study will sign the IRB-approved informed consent prior to any study-specific testing or administration of the questionnaire. Each subject will choose to receive the same lens type in both eyes, either the TECNIS Toric IOLs (Models ZCT300 and/or ZCT400), or the non-toric control IOL (TECNIS Model ZCB00).

VISIT SCHEDULE: All subjects are intended to have bilateral cataract surgery with the second-eye surgery occurring within approximately 1 month of the first-eye surgery ( $\leq 60$  days). Two postoperative study visits will be conducted; at 1 month

(30-60 days after the second-eye surgery) and at 6 months (120-180 days after the second-eye surgery) for both eyes together. However, subjects who underwent an IOL repositioning procedure due to IOL misalignment or who reported a severe visual distortion at 6 months will return for a final visit at 1 year (330-420 days after the second-eye surgery) postoperatively.

PREOPERATIVE PROCEDURES: Following informed consent, a subject questionnaire for determination of visual distortions will be administered (Patient Reported Visual Distortion Questionnaire; PRVDQ). Demographic, general preoperative and operative information will be collected from routine cataract evaluation examinations and surgical reports.

POSTOPERATIVE PROCEDURES: At the 1-month visit, a spectacle and/or contact lens prescription will be offered to each subject. If the subject has a spontaneous report of any of the 5 defined visual distortion items of interest or of blurred or hazy vision, the questionnaire will be administered and, for subjects with toric IOLs, keratometry and toric IOL axis measurements will be performed.

At the 6-month visit, the postoperative procedures will include a subject questionnaire (Patient Reported Visual Distortion Questionnaire; PRVDQ) for determination of visual distortions, biomicroscopic slit-lamp examination for any adverse events and, for subjects with toric IOLs, determination of toric IOL axis position and keratometry.

If outside of a scheduled study visit, a subject has a spontaneous report of; 1) any of the 5 defined visual distortion items of interest or 2) blurred or hazy vision at 1 month postoperatively or later, the PRVDQ questionnaire will be administered and, for subjects with toric IOLs, keratometry and toric IOL axis measurements will be performed. Exam details will be documented on an unscheduled visit form.

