4.2 Other Visual Distortion Endpoints Related to Severe Visual Distortions

In addition to the above information related to the primary endpoint analysis, other analyses will also be performed for severe visual distortion rates (based on the 5 defined items) and will include the frequency and proportion with severe visual distortions. Severe visual distortion data for the overall circumstance will be reported for the low (ZCT300) and high cylinder (ZCT400) subgroups for bilateral subjects to evaluate if there is a trend of increasing severity for the higher cylinder IOL group. The severe visual distortion rate will also be reported by IOL group for all subjects (bilateral plus those implanted in one eye (with a cataract, phakic or having another IOL in the fellow eye). In addition, an analysis including all subjects using imputed data for subjects with no questionnaire data available at any visit will also be reported.

Additional analyses including covariates will also be performed for bilateral subjects. A logistic regression model with overall severe visual distortion rates as the dependent variable and IOL group, age, gender, race, cylinder power (low- vs high-cylinder subgroups) and the interaction of age with IOL group and gender with IOL group as independent variables will be performed to further evaluate the influence of these variables on severe visual distortions. If covariates are shown to be important then additional analyses will be provided for those covariates. Results for severe visual

distortions will also be reported by study site for each IOL group. Although there are a large number of sites, any unusual patterns will be noted (i.e. all severe visual distortions at 1 or 2 sites) and further analyses performed to address any site issues.

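### The MCMC imputation planned for the severe-distortion endpoint is a normal-model method that does not suit a yes/no outcome expected in 1–2% of subjects, and the missing-at-random check beside it has no stated method

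*SAP*

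**What the plan says.** The primary endpoint (SAP 1 and 4.1) is one yes/no value per subject: any of five questionnaire items rated severe overall at 6 months. The test compares the upper limit of a two-sided 90% interval for toric minus control with 0.10. Neither SAP 4.1 nor Protocol 20.2 names the interval method.

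SAP 2.1 handles missing data in three layers.

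- **Primary analysis:** an earlier postoperative questionnaire is carried forward.
- **Secondary set:** "an additional analysis population will be evaluated that includes all subjects with last observation carried forward for missing data", with imputation added for "subjects with no available data at any time point". For these, "Imputation for those with no data will be performed using MCMC multiple imputation techniques", and this is "implemented using the MI and MIANALYZE procedures". SAP 4.2 describes the same item as "an analysis including all subjects using imputed data for subjects with no questionnaire data available at any visit will also be reported".
- **Sensitivity:** "Sensitivity analyses will be performed for severe visual distortions based on the 5 defined items for the final data analysis", in order to examine the missing-at-random assumption. No method is given.

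The SAP does not state which variable is imputed (the composite or the 0–3 item scores), which covariates enter, whether arms are imputed separately, or whether values are rounded.

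On data collection, the Protocol synopsis says of the preoperative visit: "Following informed consent, a subject questionnaire for determination of visual distortions will be administered". After surgery, Protocol 11.5 and Appendix A require the questionnaire from everyone only at month 6. Before that it is given only on a spontaneous visual complaint or before a repositioning procedure.

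**The concern.** Two features of the plan meet badly.

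First, a subject who has no complaint and misses month 6 has no postoperative questionnaire to carry forward. Under the protocol's 10% dropout allowance this could be up to about 17 toric and 13 control subjects. They drop out of the primary analysis, and only the imputed analysis and the unspecified sensitivity analyses can address them.

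Second, the named method draws from a normal distribution. The SAP does not say so; it is a property of MCMC in the named procedure. With a mean near 0.01–0.02, a normal model gives values that are either negative about half the time or, once rounded, almost always non-severe. If an arm has no observed event and is imputed on its own, its variance is zero and every imputed value is zero.

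At stake is the value of the robustness check. It should show how the result responds to plausible outcomes in the missing subjects. Here it may do little more than add non-severe subjects to both denominators.

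**Working it through.** **1. Inputs.** Event rates of 1% in both arms (Protocol 20.6) and 2% (SAP 7); margin 0.10 and two-sided 90% interval (Protocol 20.2, SAP 4.1); 169 toric and 125 control implanted, 152 and 112 evaluable (Protocol 20.6).

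**2. The plan's own figures.** 152/0.9 = 168.9 and 112/0.9 = 124.4, which round up to 169 and 125. The missing numbers are therefore 169 − 152 = 17 and 125 − 112 = 13. For the stated power with 37 and 27 subjects at 1%: SE = √(0.0099/37 + 0.0099/27) = 0.0252, and power = Φ(0.10/0.0252 − 1.645) = Φ(2.33) = 99.0%. Exact enumeration of the Wald rule gives 94.9%. The claim of more than 90% reproduces on this basis; using the variance under the null would give 65%. That choice does not affect what follows.

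**3. Normal draws for a rare yes/no outcome.** SD = √(p(1 − p)).

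| Rate | SD | P(draw < 0) | P(draw ≥ 0.5) | Events expected among 17, rounded | Events expected among 17, at rate p |
|---|---|---|---|---|---|
| 1% | 0.0995 | 46% | 4.2e-7 | 0.000007 | 0.17 |
| 2% | 0.140 | 44% | 3.0e-4 | 0.005 | 0.34 |

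Letting the model parameters vary between imputations raises the rounded count at 1% only to 0.006.

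**4. Arms without an event, at 1%.** 0.99^152 = 0.217; 0.99^112 = 0.324; both arms 0.99^264 = 0.070. At least one arm: 0.217 + 0.324 − 0.070 = 0.471.

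**5. Effect on the upper limit.** Simulation of 1,500 trials per row, 20 imputations, 152 + 17 toric and 112 + 13 control, data missing completely at random, imputation by arm without covariates, Wald-type limits. Entries are mean upper limits in percentage points.

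| True rates, toric/control | Complete cases | Normal, unrounded | Normal, rounded | Binary (beta-binomial) | Trials with rounded limit above complete-case limit |
|---|---|---|---|---|---|
| 1%/1% | 1.93 | 1.94 | 1.74 | 2.03 | 2% |
| 2%/2% | 2.76 | 2.77 | 2.51 | 2.81 | 3% |
| 2%/1% | 3.32 | 3.33 | 3.02 | 3.39 | 1% |
| 5%/1% | 7.22 | 7.23 | 6.86 | 7.26 | 3% |
| 8%/2% | 10.18 | 10.20 | 10.03 | 10.21 | 26% |
| 1%/2% | 1.41 | 1.41 | 1.26 | 1.47 | 11% |
| 1%/5% | −0.44 | −0.42 | −0.50 | −0.40 | 33% |

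- *Unrounded:* the mean difference matches complete cases (3.98 and 3.98 points at 5%/1%), and the limit rises in 49–54% of trials.
- *Rounded:* the mean limit falls by 0.19, 0.25, 0.30 and 0.36 points in the first four rows and by 0.15 at 8%/2%.
- *Decision:* every method passes in 100% of trials when both rates are 1–2%. At 5%/1% the pass rate goes from 88.1% (complete cases) to 90.1% (rounded).

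**6. One worked case.** Suppose 2/152 toric and 1/112 control are severe. The 90% score upper limit is 3.1 points. With all 30 missing subjects filled in as non-severe (2/169 and 1/125) it is 2.8.

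**7. What a tipping-point analysis would show.** In the same case, count k of the 17 missing toric subjects and none of the 13 missing controls as severe, and recompute for (2 + k)/169 against 1/125.

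| k | Score upper limit | Wald upper limit |
|---|---|---|
| 9 | 9.7 | 9.1 |
| 10 | 10.4 | 9.8 |
| 11 | 11.1 | 10.5 |

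Non-inferiority is lost at k = 10 by the score interval (10/17 = 59%) and at k = 11 by Wald (11/17 = 65%).

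**The case against.** The strongest reply is that the harm depends on choices the SAP leaves open. It prescribes neither rounding nor imputation by arm, and MIANALYZE can combine a proportion as a mean without rounding. This is an additional analysis, the same paragraph commits to reporting the extent of missingness and to missing-at-random sensitivity analyses, and the effect is small against a 10-point margin. All of that stands, and it limits the point to the choice and specification of method.

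Three stronger readings are tempting, and the documents do not support them.

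- **A reader might infer that the check can only favour the toric lens.** Unrounded draws do not bias the difference under missing at random. Rounding shrinks both arms, so it can count against toric when control is worse: with 1/152 against 5/112 the score limit moves from −0.86 to −0.76 points.
- **A reader might infer that no subject qualifies for imputation,** because the questionnaire is mandatory before surgery. That follows only from the literal wording. SAP 2.1 defines the primary population by month-6 data or a prior postoperative visit, so postoperative data are evidently meant. The wording still needs tightening.
- **A reader might infer that imputation is the only protection against 30 missing subjects.** The sensitivity analyses are a second one, though without a method. The 30 is also an upper bound: Protocol 11.7 anticipates at most 10% loss, and some of these subjects will have an earlier postoperative questionnaire.

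What remains is that a normal model is a poor choice for this outcome and that a better one costs almost nothing.

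**Conclusion.** The point holds as a weakness in a secondary analysis that should be corrected. It does not threaten the primary conclusion: at the planned 1–2% rates every version of the imputation passes.

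Its size depends on the unstated rounding rule. With rounding, almost no events are imputed and the upper limit usually falls by about 0.2–0.4 points when toric is no better than control. Without rounding there is no systematic shift, but nearly half the imputed values are impossible. Under by-arm imputation at 1%, 47% of trials have at least one arm whose model has zero variance.

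The figures assume that all 17 and 13 dropouts lack postoperative data, that the composite is imputed by arm without covariates, and that data are missing completely at random. That MCMC in SAS MI is a normal-model method is method knowledge and not a statement in the SAP. The 2/152 against 1/112 case is illustrative.

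**What to change.** In SAP 2.1 and 4.2:

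1. Define the imputed set as subjects with no postoperative questionnaire.
2. Replace MCMC with binary imputation of the five-item composite, using a method that tolerates an arm with no events. Two examples are a beta-binomial draw (each arm's rate from Beta(x + 0.5, n − x + 0.5), then Bernoulli outcomes) and penalised logistic imputation. State the covariates and the handling of arms.
3. Specify the missing-at-random sensitivity analysis as a tipping-point grid. Let the number counted as severe run from zero to the actual number missing in each arm, recompute the primary interval in every cell, and report where non-inferiority is lost. Name the interval in SAP 4.1, because the tipping point depends on it.

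The cost is SAP wording and a short program, with no new data. The imputed upper limit may be slightly less favourable (2.03 against 1.74 points for rounded draws at 1%/1%). In return, the grid can show how extreme the missing outcomes would have to be to overturn the result.
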